### **6.2.2 12-Lead Electrocardiogram**

The 12-lead ECG will be collected as described in the protocol. The following ECG parameters are calculated: HR and PR, QRS, QT and QTcF intervals (if not available, QTcF = QT/(RR0.33)).

### **6.2.3 Vital Signs**

Supine vital signs, including HR, BP, and temperature are collected during this study at the intervals described in the protocol.

### **6.2.4 Physical Examination**

A physical examination, including body weight (Screening and EOS) and height (Screening only), and assessments of the head, eyes, ears, nose, throat, skin, neurological, lungs, cardiovascular system, abdomen, and lymph nodes will be conducted.

## 6.2.5 Clinical Laboratory Evaluations

All blood and urine analyses will be conducted on-site or at a central laboratory at the sampling times indicated in the Schedule of Assessments. For abnormal values, additional testing may be performed, or clinical laboratory evaluations may be added to evaluate the abnormal values.

## 6.2.6 Columbia-Suicide Severity Rating Scale (C-SSRS)

The C-SSRS is a semi-structured interview designed to assess the severity and intensity of suicidal ideation, suicidal behavior and non-suicidal self-injurious behavior over a specified time period. The measurement of suicidal ideation is based on five ‘yes’ or ‘no’ questions with accompanying descriptions arranged in order of increasing severity. If the participant answers ‘yes’ to either questions 1 or 2, the intensity of ideation is assessed in five additional questions related to frequency, duration, controllability, deterrents and reasons for the most severe suicidal ideation. Suicidal behavior is assessed by asking questions categorizing behaviors into actual, aborted and interrupted attempts; preparatory behavior, and non-suicidal self-injurious behavior.

The C-SSRS is made up of ten categories, all of which maintain binary responses (yes/no) to indicate a presence or absence of ideation (Category 1-5) or behavior (Category 6-10). The ten categories included in the C-SSRS are as follows:

- Category 1 – Wish to be Dead;
- Category 2 – Non - specific Active Suicidal Thoughts;
- Category 3 – Active Suicidal Ideation with Any Methods (Not Plan) without Intent to Act;
- Category 4 – Active Suicidal Ideation with Some Intent to Act, without Specific Plan;
- Category 5 – Active Suicidal Ideation with Specific Plan and Intent;
- Category 6 – Preparatory Acts or Behavior;
- Category 7 – Aborted Attempt;
- Category 8 – Interrupted Attempt;
- Category 9 – Actual Attempt (non-fatal);
- Category 10 – Completed Suicide.

A yes/no binary response is also utilized in assessing Self - injurious Behavior without Suicidal Intent.

C-SSRS Suicidal ideation scores is a numerical score derived from the C-SSRS categories (the maximum suicidal ideation category (1-5 on the CSSRS) present at the assessment. A score of 0 is assigned if no ideation is present.). The score is created at each assessment for each participant and is used for determining treatment emergence. A C-SSRS ideation score of 4 or 5 is termed ‘serious ideation’, > 0 is termed ‘positive ideation’.

Suicidal ideation: A “yes” answer at any time from first administration of study drug to any one of the five suicidal ideation questions (Categories 1-5) on the C-SSRS. Suicidal behavior: A “yes” answer at any time from first administration of study drug to any one of the five suicidal behavior questions (Categories 6-10) on the C-SSRS. Suicidal ideation or behavior: A “yes” answer at any time from first administration of study drug to any one of the ten suicidal ideation and behavior questions (Categories 1-10) on the C-SSRS.

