## 6.2 Exclusion Criteria

1. Participant has a primary diagnosis of any other DSM-5 disorder, as assessed by the MINI Version 7.0.2.
2. Participant has a body mass index (BMI)  $<18 \text{ kg/m}^2$  or  $\geq 40 \text{ kg/m}^2$ .
3. Participant is known (or meets DSM-5 criteria for moderate or severe substance use disorder [mild substance use disorder may be allowed, after consultation with the sponsor, if use of the substance is unlikely to confound the study results]) to abuse illegal drugs or has a positive urine test for illegal drugs at Screening, Baseline, or prior to dosing on Day 1. The Investigator must confirm the participant is not otherwise impaired prior to dosing on Day 1.
4. Known history of:
  - a. Hepatitis B,
  - b. Hepatitis C, or
  - c. Infection with human immunodeficiency virus.
5. Participant smokes an average of  $>10$  cigarettes and/or e-cigarettes per day.
6. Abnormal LFTs at Screening:
  - a. AST, ALT or gamma-glutamyl transferase (GGT)  $>2 \times$  the ULN.

- b. Total bilirubin levels  $>1.5 \times$  the ULN (participants with a diagnosis of Gilbert's syndrome with high unconjugated bilirubin are eligible provided they meet other LFT criteria).
7. Moderate to severe renal impairment at Screening, with an estimated glomerular filtration rate (eGFR) of  $\leq 80$  mL/min according to the Cockcroft-Gault equation.
8. Active suicidal ideation and/or intent within 2 months of Screening, indicated by a 'Yes' response to suicidal ideation question 4 or 5 on the C-SSRS.
9. Any history of suicidal behavior within the last 5 years (excluding suicidal ideation):
  - a. Medical history of suicide attempt, or
  - b. 'Yes' response to the following suicidal behavior questions on the C-SSRS:
    - i. actual attempt, or
    - ii. interrupted attempt, or
    - iii. aborted attempt.
10. Uncontrolled hypertension at Screening (after 5 minutes rest):
  - a. SBP  $>140$  mmHg, or
  - b. DBP  $>90$  mmHg.
11. Resting heart rate at Screening of  $\geq 90$  bpm (after 5 minutes rest).
12. Have any history, physical or psychological symptoms, medication or other relevant findings that would make a participant unsuitable for the study based on the clinical judgement of study personnel. This would include (but is not limited to):
  - a. A need to continue active psychotherapy or pharmacotherapy during the study period.

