### **8.1.3 Definition of Baseline**

Baseline values will be defined as the worst measurement prior to the initiation of study treatment (or last non-missing if only one measurement was taken), unless specified otherwise for the corresponding endpoint.

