### **8.2.3.2 Baseline Characteristics**

Summary of duration of PTSD symptoms (in years, from CAPS-5 conducted at screening), age at end date of index trauma, time since end date of index trauma (years = (ICF date-end date of index trauma+1)/365.25), type of traumatic event (PT MedDRA coding of index event), prior PTSD treatment type, prior psychedelics used, and dissociative PTSD symptoms (Yes = Item 29 or 30 have a severity  $\geq 2$ ) will be summarized.

Lifetime C-SSRS (Lifetime accounts for all suicidal ideation and behavior prior to the study): positive lifetime suicidal ideation (ideation score  $>0$ ), serious lifetime suicidal ideation (ideation score of 4 or 5), positive lifetime suicidal behavior (behavior score  $>0$ ) will be summarized. The same summary for past 2 months suicidal ideation and past 5 years suicidal behavior will be presented.

Data listings will include the information of PTSD duration and other baseline characteristics.

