### 8.4.3 Vital Signs

**Per dosing session:** Baseline is defined as the measurements of pre-initial dose during each dosing session.

**Per participant:** Baseline is defined as the measurements collected at Visit 2. Post-baseline vitals were collected at Visit 15.

Where multiple values are recorded at a time for a participant, the mean of the values will be used in the descriptive statistics.

Descriptive statistics for the measured values and change from baseline will be calculated and plotted for each parameter by treatment and timepoint.

Vital signs (SBP, DBP, HR, respiratory rate and body temperature) will be listed for individual participants.

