### 8.4.6 C-SSRS

The number and percentage of subjects with suicidal ideation (Category 1-5) or suicidal behavior (Category 6-10), and Self-injurious behavior without suicidal intent based on the C-SSRS after first administration of study drug will be summarized.

Two shift tables will demonstrate changes in C-SSRS, most severe suicidal ideation (0 to 5), and C-SSRS categories (No suicidal ideation or behavior, suicidal ideation, suicidal behavior) from baseline to post-treatment.

C-SSRS results will be listed for individual participants.

[REDACTED]

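### The C-SSRS has no baseline of its own, so the worst-value default can bring lifetime history into the two suicidality shift tables and mask worsening there

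*SAP*

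**What the plan says.** SAP 8.1.3 sets the general rule: "Baseline values will be defined as the worst measurement prior to the initiation of study treatment". It yields only where a section sets its own baseline ("unless specified otherwise for the corresponding endpoint"). Vital signs do so in SAP 8.4.3 (per participant, "Baseline is defined as the measurements collected at Visit 2"), and SAP 8.4.4 does so for the ECG. SAP 8.4.6 does not do so for the C-SSRS, yet it plans baseline-to-post-treatment shifts: "Two shift tables will demonstrate changes in C-SSRS, most severe suicidal ideation (0 to 5), and C-SSRS categories". The second table has three levels: neither ideation nor behavior, ideation, and behavior.

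SAP 6.2.6 defines the ideation score as "the maximum suicidal ideation category (1-5 on the CSSRS) present at the assessment", with 0 for none, and adds: "The score is created at each assessment for each participant and is used for determining treatment emergence". It does not say how emergence is determined.

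SAP 8.2.3.2 summarizes lifetime ideation and behavior as baseline characteristics, using the same ideation score, and explains: "Lifetime accounts for all suicidal ideation and behavior prior to the study". It also summarizes ideation over the past 2 months and behavior over the past 5 years.

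**The concern.** The worst-value default is workable for a scale measured over one fixed, recent window. The C-SSRS is different: before dosing it is recorded over several recall periods, one of them the whole of life. Read literally, the default picks the worst of these, and by construction that is the lifetime value. A lifetime maximum would then be compared with roughly ten weeks on study.

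Eligibility leaves room for this to matter. Protocol 6.2 excludes ideation at levels 4 or 5 only within 2 months of Screening, and the listed suicide attempts only within 5 years. Older and more severe history is allowed.

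Suicide-risk events are of special interest in both documents, and Protocol 4.4 presents the placebo control as a means of judging suicidality objectively. The shift tables are the only planned C-SSRS summaries that measure change from a participant's own starting point. Masking would occur in both arms, so its likely effect is to shrink any difference between them, with about 32 participants per arm.

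**Working it through.** The plan gives no figure on this point, so there is none to reproduce. The check reads the sections together and then counts score patterns.

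**Which baseline governs.** SAP 8.1.3 applies unless overridden. SAP 8.4.3 and 8.4.4 override it; 8.4.6 does not. The default therefore governs both C-SSRS shift tables.

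**Which values are eligible.** The C-SSRS is given before dosing at Screening, Baseline and Day 1 (Protocol 1.3 and 4.2). SAP 8.2.3.2 derives lifetime, past-2-month and past-5-year results. SAP 8.1.3 does not say which of these count as measurements.

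**Ideation table (0 to 5).** Let r be recent pre-dose ideation, l the lifetime score and p the worst post-dose score.

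- r = 0 to 3. Exclusion 8 bars recent 4 or 5; I assume none arises between Screening and the first dose.
- l = r to 5, since lifetime includes the recent period.
- p = 0 to 5. Worsening from the recent level means p > r.
- With a lifetime baseline the upward shift is lost when r < p ≤ l.

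For each r there are (6 − r) values of l and (5 − r) worsening values of p. Worsening patterns number (6 − r)(5 − r). Masked patterns number the sum of (l − r) over l, which is (5 − r)(6 − r)/2.

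| r | Worsening patterns | Upward shift lost |
|---|---|---|
| 0 | 6 × 5 = 30 | 15 |
| 1 | 5 × 4 = 20 | 10 |
| 2 | 4 × 3 = 12 | 6 |
| 3 | 3 × 2 = 6 | 3 |
| Total | 68 | 34 |

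*Post-dose score 4 or 5.* There are 6 + 5 + 4 + 3 = 18 pairs (r, l), giving 18 × 2 = 36 patterns. For each of the four values of r, l = 4 loses p = 4 and l = 5 loses both, so 4 × 3 = 12 are masked.

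*Post-dose score 1 to 3.* The remainder is 68 − 36 = 32 patterns, of which 34 − 12 = 22 are masked.

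The effect on one participant depends on the lifetime score:

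| Lifetime score | Post-dose scores that can register as an upward shift |
|---|---|
| 0 | 1 to 5 |
| 1 | 2 to 5 |
| 2 | 3 to 5 |
| 3 | 4 and 5 |
| 4 | 5 |
| 5 | none |

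**Three-level table.** With a lifetime baseline, a participant whose suicidal behavior was more than 5 years ago starts in the top row.

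- New category 3 ideation on treatment reads as a move from behavior to ideation, an apparent improvement. The separate 0-to-5 table would show an upward shift only if that person's lifetime ideation score were below 3.
- A new attempt reads as behavior to behavior, with no shift.

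**With a recent-window baseline.** Baseline equals r, so all 68 patterns show an upward shift. The post-dose incidence summary counts all 68 under either baseline, because any positive answer after the first dose qualifies.

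**The case against.** The best reply is that the lifetime reading is not the intended one. A measurement most naturally means one taken at a visit; SAP 6.2.6 scores what is present at the assessment; SAP 8.2.3.2 keeps lifetime history apart as a descriptor. No section expressly puts lifetime recall into the shift tables. The table shells are in a separate file and may settle the matter.

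This shows that the lifetime baseline is one reading of the text, not a stated choice. It does not remove the problem. SAP 8.2.3.2 derives a lifetime ideation score under the heading of baseline characteristics, it predates dosing, and SAP 8.1.3 asks for the worst value. Two programmers could follow the text faithfully and produce different tables.

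A reader might go further and infer that the plan hides treatment-emergent suicidality, or that the shift tables cannot show new ideation at all. The documents do not support either inference:

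- SAP 8.4.6 counts everyone with ideation, behavior or self-injury after the first dose, whatever their history, and lists all results.
- Protocol 7.6 sends ideation at levels 4 or 5, and any suicidal behavior, to adverse event reporting, and suicide-risk events are of special interest.
- The dosing and enrollment criteria in Protocol 4.8 and 4.9 look at the period since the last administration, so this baseline does not affect them.
- Even with a lifetime baseline, the post-dose axis of the shift table still shows the on-treatment category. Only the upward shift is lost, and only where the post-dose score does not exceed the past worst.

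It is also fair that randomization balances history in expectation, so post-dose incidence can be compared between arms without a baseline. But incidence does not separate new or worsened ideation from persisting ideation. For questions 1 to 3, Protocol 7.6 leaves adverse event reporting to clinical judgement. At those levels the shift table does work that no other planned summary does.

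**Conclusion.** The point holds as a moderate defect in the shift tables and in any treatment-emergence determination, and should be corrected. The default baseline applies to the C-SSRS by omission, its look-back is unlimited, and a literal reading can select lifetime history. The missing emergence rule is a gap under any reading.

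Under the lifetime reading, half of the worsening patterns (34 of 68) lose their upward shift, and a participant with behavior more than 5 years ago cannot shift upward in the three-level table. The masking is heaviest at post-dose scores 1 to 3 (22 of 32 patterns, against 12 of 36 at scores 4 or 5), where adverse event reporting is discretionary.

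The counts give every pattern equal weight and assume that recent pre-dose ideation is at most 3. They are not rates: the documents do not say how many participants have a worse lifetime history, so the number affected cannot be estimated. Those masked must also have post-dose ideation above their recent level but no higher than their lifetime level.

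**What to change.** In SAP 8.4.6, override 8.1.3 for the C-SSRS:

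1. **Baseline.** The worst category over past-2-month ideation and past-5-year behavior at Screening, together with the Baseline and Day 1 pre-dose assessments. Use it in both shift tables.
2. **Treatment-emergent ideation.** A post-dose ideation score above that baseline.
3. **Treatment-emergent behavior.** Any post-dose suicidal behavior, whatever the baseline row. Exclusion 9 names actual, interrupted and aborted attempts but not preparatory acts, so someone with recent preparatory acts could still start in the top row.
4. **Lifetime history.** Keep it as a descriptive baseline characteristic in 8.2.3.2 only.

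Point 6.2.6 to this rule, make the table shells agree, and settle the wording before the randomization code is opened.

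The cost is a few sentences and some programming; no new data are needed, since 8.2.3.2 already summarizes both recent windows. The downside is that some recurrences of old symptoms will count as emergent. The lifetime summary lets readers see that history.

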## 7 HANDLING OF MISSING VALUES

### 7.1 Efficacy Analysis

The efficacy analysis will be conducted using the available data without any statistical imputation for missing data for data lost to follow up or otherwise unavailable. As for scales, if any item is

missing, any total or sum involving that item will be considered missing. As SDS total score is calculated as a mean of the domains, up to 1 of 3 questions can be missing per scale design.

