## **10 DATA HANDLING AND RECORD KEEPING**

### **10.1 Collection of Data**

Data collected from each completed participant will be recorded on source documents, which will be entered into an eCRF. The Investigator is responsible for ensuring that all sections of the eCRF are completed correctly and that entries can be verified against the source documents. If certain data are not available or not applicable this will be indicated as such within the appropriate area of the eCRF.

Screening failures are defined as participants who signed consent to take part in the study but were not subsequently assigned to study intervention. Screening failures may fail to meet any inclusion criteria and may meet one or more exclusion criteria or withdraw consent prior to enrollment. All potential participants who begin Screening will be tracked on a Screening Log. Screening failures are not considered evaluable. Minimal data on screening failures will be recorded in the clinical study database. A minimal set of screen failure information is required to ensure transparent reporting of screen failure participants to meet the CONSORT publishing requirements and to respond to queries from regulatory authorities. Minimal information includes demography, screen failure details, eligibility criteria, and any SAEs.

Data produced by automatic devices with original printouts (i.e., clinical laboratory evaluation results, ECG traces) will be attached to the source documents. Clinical laboratory parameters will be provided in laboratory printouts which are to be signed by the Investigators. Comments on all clinically significant abnormal values will be provided and documented by the Investigators or appropriately recorded within the eCRF.

Adverse Events and Medical History will be reported by the MedDRA SOC and PT; the most current version at the time of study start will be applied to all terms. All Medical History and AEs will be included in the data listings. Furthermore, all Prior Medications and Concomitant Medications will be reported using the WHODRUG categorization; the most current version at the time of study start will be applied to all terms.

All Prior Medications and Concomitant Medications will be summarized within the data listings.

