## **6 ENDPOINTS AND COVARIATES**

### **6.1 Efficacy Assessments**

#### **6.1.1 Clinician-Administered PTSD Scale for DSM-5 (CAPS-5)**

The CAPS-5 is a 30-item structured interview that can be used to: Make a current diagnosis of PTSD; Assess change in PTSD symptoms over time.

In addition to assessing the 20 DSM-5 PTSD symptoms, questions target the onset and duration of symptoms, subjective distress, impact of symptoms on social and occupational functioning, improvement in symptoms since a previous CAPS administration, overall response validity, overall PTSD severity and specifications for the dissociative subtype (depersonalization and derealization). The CAPS-5 also rates intrusion symptoms (intrusive thoughts or memories), avoidance, cognitive and mood symptoms, arousal and reactivity symptoms, duration and degree of distress.

The CAPS-5 total severity score (primary efficacy measure) is calculated by summing severity scores for items 1-20. CAPS-5 severity scores range from 0-80 points, with higher scores indicating greater PTSD symptom severity.

The CAPS-5 symptom cluster severity scores are calculated by summing the individual item severity scores for symptoms contained in a given DSM-5 cluster. Thus, the Criterion B (intrusion) severity score is the sum of the individual severity scores for items 1-5; the Criterion C (avoidance) severity score is the sum of items 6 and 7; the Criterion D (cognitions and mood) severity score is the sum of items 8-14; and the Criterion E (arousal and reactivity) severity score is the sum of items 15-20. A symptom cluster score may also be calculated for dissociation by summing items 29 and 30.

PTSD diagnostic status is determined on the CAPS-5 by first dichotomizing individual symptoms as “present” or “absent” then following the DSM-5 diagnostic rule. A symptom is considered present only if the corresponding item severity score is rated 2=Moderate/threshold or higher otherwise a symptom is considered absent. The DSM-5 diagnostic rule requires the presence of least one Criterion B symptom, one Criterion C symptom, two Criterion D symptoms, and two Criterion E symptoms. Criterion G requires a rating of 2=moderate or higher on items 23-25.

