#### **6.1.5 PTSD Checklist for DSM-5 (PCL-5)**

The PCL-5 is a 20 item self-report measure that assesses the presence and severity of the 20 DSM-5 symptoms of PTSD. Participants rate each item from 0 ('not at all') to 4 ('extremely') to indicate the degree to which they have been affected by that particular symptom over the past week.

A total symptom severity score ranges from 0 to 80, with higher scores representing more severe symptoms.

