#### **6.1.7 Beck Depression Inventory-II (BDI-II)**

The BDI-II is a 21-item self-report measure assessing depressive symptoms and their severity. Items include hopelessness and irritability, cognitions such as guilt or feelings of being punished, as well as physical symptoms such as fatigue and weight loss. Each item is rated on a 4-point scale, from 0 to 3. Items are summed to create a total score.

A total score ranging from 0 to 63 is possible, with higher scores indicating higher levels of depression.

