### **8.1.7 Covariates**

For the analysis of select efficacy endpoints, the baseline value will be included (if applicable) as a covariate. Sex will also be used as a covariate.

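### SAP 7.1 voids a whole scale total for one blank item; for BDI-II and WEMWBS a single blank at Baseline removes the participant from that endpoint's MMRM at every visit (low severity)

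*SAP*

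**What the plan says.** SAP 7.1 analyses efficacy "using the available data without any statistical imputation for missing data for data lost to follow up or otherwise unavailable". At item level, one blank is enough for the scale score to go: "any total or sum involving that item will be considered missing". The one exception is the SDS, scored as a mean of its domains, where "up to 1 of 3 questions can be missing per scale design".

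The scales caught by the rule are long:

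- CAPS-5 total (SAP 6.1.1): "is calculated by summing severity scores for items 1-20".
- PCL-5 (SAP 6.1.5): "The PCL-5 is a 20 item self-report measure".
- BDI-II (SAP 6.1.7): 21 items, and "Items are summed to create a total score".
- WEMWBS (SAP 6.1.8): 14 items, summed.

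The MMRM sample code in SAP Appendix 3 models change from baseline with the baseline score on the right-hand side. SAP 8.1.7 says the same of the covariate: "the baseline value will be included (if applicable) as a covariate". SAP 8.1.3 takes the worst pre-dose measurement as baseline, or the only one if just one was taken.

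In the Schedule of Assessments (Protocol 1.3), PCL-5 is completed at Screening and at Baseline. BDI-II and WEMWBS are completed before dosing only at Baseline, and then at Days 17, 29, 43 and 64 (plus early termination).

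**The concern.** The rule is uneven. An SDS score stands with a third of its domains absent, while a BDI-II with 20 of 21 items answered does not. The SAP attributes the SDS allowance to the design of that scale and gives no reason for zero tolerance elsewhere.

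The costlier case is a blank at Baseline. A lost follow-up total can be partly offset, because an MMRM uses the participant's other visits. A lost baseline total cannot be offset. Without it there is no change score at any visit and no covariate value, so every later form that participant completed for that scale goes unused. Among the scales for which proration is proposed here, this affects BDI-II and WEMWBS.

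At stake is avoidable loss of precision on self-report secondary endpoints in a trial planned around 27 evaluable participants per arm. According to the SAP, the results will be used to design and power later trials.

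**Working it through.** **Plan's own figures.** Protocol 9.2 and SAP 4: difference 11, SD 12, so d = 11/12 = 0.92. A two-sample noncentral t calculation at two-sided 0.05 needs 19.7 per arm for 80% power and 26.01 for 90%. This reproduces the stated 20 (power 80.6%) and 27 (91.1%). With 15% dropout, 27/0.85 = 31.8, hence 32 per arm and 64 in total. At the one-sided 0.05 level of SAP 8.1.6, 27 per arm gives 95.3%.

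**Step 1: chance that a total is lost at one visit.** Let k be the number of items and q the chance that an item is blank. With independent blanks, P(lost) = 1 - (1 - q)^k. The documents do not give q; 0.25% to 1% is an assumed range.

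| Scale length | q = 0.25% | q = 0.5% | q = 1% |
|---|---|---|---|
| 14 (WEMWBS) | 3.4% | 6.8% | 13.1% |
| 20 (PCL-5) | 4.9% | 9.5% | 18.2% |
| 21 (BDI-II) | 5.1% | 10.0% | 19.0% |

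Out of 64 participants, that is 2.2 to 8.4 WEMWBS totals, 3.1 to 11.7 PCL-5 totals and 3.3 to 12.2 BDI-II totals per visit. If blanks cluster in the same people, fewer forms are affected at the same q.

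**Step 2: the Baseline form.**

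- BDI-II and WEMWBS: one pre-dose form. The Step 1 percentage is also the share of participants who leave that scale's MMRM altogether.
- PCL-5: two pre-dose forms. If the Baseline form has a blank, the Screening total is still a pre-dose measurement and SAP 8.1.3 would use it.
- CAPS-5: administered by a central rater, with a score of at least 28 at Baseline required for entry (Protocol 6.1). A missing Baseline total should therefore be rare.

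**Step 3: effect on power, for scale only.** For a scale with one pre-dose form, count only participants with both a Baseline and a Week 10 total. If a fraction f of forms has a blank, n per arm = 27 × (1 - f)².

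- f = 5%: 27 × 0.9025 = 24.4
- f = 10%: 27 × 0.81 = 21.9

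One-sided 0.05 power at d = 0.92 goes from 95% to 93% and 91%. At an assumed smaller effect of 0.75, which is not in the documents, it goes from 86% to 83% and 79%. For a given f these overstate the loss, because they ignore the other visits that the MMRM uses. The planning effect was set for CAPS-5, not for these scales.

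**Step 4: what proration would recover.** Allow at most 2 blanks of 20 or 21 items, or 1 of 14. A total is then lost only if more items than that are blank. At q = 1% the binomial tail is 0.10% for 20 items, 0.12% for 21 and 0.84% for 14.

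**Step 5: what proration costs in accuracy.** With m of k items blank, equal item variances and a common inter-item correlation r, the prorating error as a share of total-score variance is

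(1 - r) × [m + m²/(k - m)] / {k × [1 + (k - 1)r]}.

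At an assumed r = 0.4:

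- 20 items: one blank 0.6 × 1.053/172 = 0.4%; two blanks 0.6 × 2.222/172 = 0.8%
- 21 items: two blanks 0.6 × 2.211/189 = 0.7%
- 14 items: one blank 0.6 × 1.077/86.8 = 0.7%

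Simulations of 20-, 21- and 14-item scales put it at about 0.4-1%. With weaker correlation (r = 0.2) the formula gives up to 1.9%, still small.

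**The case against.** The strict rule is explicit and pre-specified, and it contradicts nothing else in the plan. No instrument's proration rule appears in the documents; the only scale-design allowance cited is for the SDS. Preferring proration, and a 90% threshold, is therefore a reviewer's judgement. That stands, and it is why the fix is conditional on each instrument's scoring rules.

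The plan also has safeguards. Protocol 10.1 describes data as "recorded on source documents, which will be entered into an eCRF", but it goes on to send missing entries to the investigator as queries, to be resolved before database lock. Protocol 9.6 provides for the missing-data methods to be reassessed before lock, with sensitivity work if the extent of missing values calls for it. Form-level completion checks could be in the Data Management Plan, which is not among the documents. These points stand in part. A query cannot always recover what a participant would have answered on a given day, and the SAP specifies no item-level sensitivity analysis in its visible text. But the number of blanks may be very small.

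Finally, these are secondary endpoints in a trial that SAP 8.1.5 describes as not confirmatory, and they did not drive the sample size. That stands, and it keeps the severity low.

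**Conclusion.** The point holds for the self-report secondary scales. One blank item discards a nearly complete PCL-5, BDI-II or WEMWBS total. For BDI-II and WEMWBS, a blank at Baseline removes the participant from that scale's MMRM at every visit. Under the assumed 0.25-1% independent blanks per item, 5-19% of 20- or 21-item totals and 3-13% of 14-item totals would be lost per visit. The true figure could be near zero if blanks are prevented or resolved.

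Three stronger readings are tempting and are not supported:

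- *That a Baseline blank costs every visit on any long scale.* PCL-5 has a Screening total to fall back on, and CAPS-5 is centrally rated with a Baseline entry score. The primary endpoint is largely protected.
- *That power is materially damaged.* This needs a blank rate the documents do not give, and the larger power loss in Step 3 also needs an effect size they do not give.
- *That known CAPS-5 outcomes are being lost in numbers.* In logic, 19 answered items summing to 12 or more rule out remission (11 or below), yet the status would become missing. But an interviewer administers CAPS-5, and nothing shows that this case arises. Filling in only the certain cases would also make missingness depend on the score: with one blank item scored 0-4, sums of 7 or less and of 12 or more would be classified, while 8 to 11 would stay missing.

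This is neither an arithmetic error nor a contradiction in the plan. Severity is low.

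**What to change.** Amend the item-level sentence in SAP 7.1 as follows.

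- For PCL-5, BDI-II and WEMWBS, where the instrument's scoring rules do not forbid it: if at least 90% of items are answered (at most 2 blank of 20 or 21, at most 1 of 14), total = mean of answered items × number of items. Otherwise the total is missing. Apply this at baseline and follow-up alike.
- Report the complete-item analysis of these three scales as a sensitivity analysis.
- Keep the complete-item rule for CAPS-5 and MADRS totals, which a central rater collects.

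PSQI and PTGI fall under the same SAP sentence. This proposal does not extend to them, and a mean-of-items rule would not fit the PSQI's component scoring (SAP Appendix 1).

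The cost is a few words in the SAP, a few lines of derivation code and one extra set of tables, all before database lock. The instruments' scoring rules must be checked first. The statistical price is a person-mean assumption for at most two items per form. If the forms already force every item to be completed, a sentence in the SAP saying so would close the point.
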